After eligibility and written informed consent is confirmed patients will be randomized on the day of surgery after arrival at the OR to receive either fibrinogen concentrate or placebo after heparin reversal as indicated in the algorithm (Figure 3). If the patient has a diffuse medical bleed then the research coordinator will be called to inform The research coordinator study drug designate will call the study drug designate to randomize the patient and a sequential envelope will be opened by them in the blood bank. The drug/placebo will be prepared in the Blood Transfusion Services at the Infirmary site. The drug/placebo will be transported to the OR by the study drug designate.

Dosage and Dosage Regimen

The dose of fibrinogen concentrate will be calculated based on the point of care measurement of maximum clot firmness (MCF)

Capital Health

in the FIBTEM® test performed on CPB (aortic cross clamp off)¹⁰. According to the available literature we will use the following formula to achieve the preoperative (baseline) FIBTEM MCF (mm):

$$\text{Fibrinogen dosage (g)} = [\text{Preop FIBTEM MCF (mm)} - \text{FIBTEM MCF (mm)}] \times \text{bodyweight (kg)} \times c$$

$$C = \frac{0.5 \text{ g}}{1(\text{mm}) \times 70}$$

70

The formula can be simplified to:

$$(\text{Preop FIBTEM MCF} - \text{FIBTEM MCF}) \times \text{bodyweight}/140.$$

Calculation example: A patient's bodyweight is 75kg. The baseline FIBTEM MCF showed 22mm. The FIBTEM test on CPB shows a MCF of 10 mm. The overall dose of concentrated fibrinogen to achieve the baseline MCF of 22 mm would be:

$$\text{Fibrinogen dosage (g)} = (22 - 10) \times 75/140 = 12 \times 75/140 = \mathbf{6.4}$$

Fibrinogen dosing will be based on the results of the FIBTEM® analysis. The amount of fibrinogen concentrate corresponds to approximately 0.5 g of fibrinogen concentrate needed to raise MCF by 1 mm in a 70 kg patient^{9,10,26}. The maximum fibrinogen concentrate dose used in this study will be 10 g. If the baseline FIBTEM® is ≤ 12 mm the fibrinogen dosage will be calculated **from a minimum baseline value of 15 mm to achieve a more effective fibrinogen dosage**. In the placebo group, the standard hemostatic algorithm involving the use of plasma, Cryo and platelets (Figure 3), will be used as per the standard of care currently in place at CDHA.

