clinic at the time window of six weeks +/- 1 week, a phone visit will occur by the research coordinator. Additionally all patients will be contacted by a research coordinator at three and six months. The focus of the interviews will be to determine anginal symptoms, and ~~need for~~ **if** readmission to hospital for acute myocardial infarction (AMI), acute coronary syndrome (ACS) or congestive heart failure (CHF) **occurred**. Events of interest include: incisional wound infection, thrombosis, recurrent angina, myocardial infarction, angiography, percutaneous coronary intervention (PCI), repeat cardiac surgery, stroke and cardiac related mortality. Any patients with evidence of adverse study drug related events at follow-up will be investigated further by the Data and Safety Monitoring Committee to review all the supporting evidence.

Proposed frequency of analysis

As previously stated there will be an interim analysis performed by the data and safety monitoring committee. This analysis will be conducted when half of the patients have been enrolled. The final analysis will be conducted once all enrolled patients have reached their follow-up date. All final analysis will take into consideration that an interim analysis was conducted.

SELECTION AND WITHDRAWAL OF SUBJECTS

Inclusion criteria

Participants will be eligible to participate in this trial if they:

- are **scheduled for** elective complex cardiac surgical procedures including:
 - double procedures (aortic valve replacement (AVR)+CABG, mitral valve repair/replacement (MVR)+CABG, AVR+MVR),
 - redo-sternotomies, and
 - Aortic root repair +/-AVR.
- have a preoperative fibrinogen level of ≤ 3.8 g/l

Capital Health

Subject exclusion criteria

Participants will be excluded if they have:

- Any known congenital or pre-existing bleeding disorder,
- ~~pre-existing clinically significant abnormal fibrinogen levels~~
- ~~pre-existing clinically significant abnormal fibrinogen levels~~
- ~~pre-existing clinically significant abnormal FIBTEM MCF tests~~
- Preoperative fibrinogen level of < 1.0 g/l
- Preoperative FIBTEM[®] of < 5 mm
- Preoperative fibrinogen level of > 3.8 g/l
- severe liver disease (alanine aminotransferase or aspartate aminotransferase > 150 U/l),
- inability to provide informed consent,
- emergency surgery,
- **self-report** pregnancy or nursing,
- age under 18 years,

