The Blood Transfusion Services are able to unblind for the clinical treatment of a patient. Please refer to the site Standard operating procedure for more details of this process. If a patient's treatment is unblinded before the 24 hour primary end point their data will not be used in the analysis.

STATISTICS

Sample size

The primary outcome of interest will be overall need for blood transfusion at 24hr after surgery (including all used blood components from the start of surgery). For the sample size calculations G*Power version 3.1.2 was used.

Based on the available literature ^{9,10,12}, the investigator hypothesized a 70-90% reduction in total units of blood products in the group receiving fibrinogen compared with the group receiving conventional therapy. An estimate of blood product requirement in the group receiving conventional therapy is mean 3.4 units (standard deviation 5.9) based on our data from 2005 to 2007 for AVR+CABG, MVR+CABG, AVR+MVR, and Aortic root repair +/-AVR. Standard deviation 5.9 was used for both groups. Blood product requirement in the two groups will be compared using the Mann-Whitney U test for two independent samples. The sample size calculation was based on a two-tailed test with $\alpha = 0.05$, for $\beta = 0.2, 0.1, \text{ and } 0.05$. The sample sizes shown Table 1 represent the number of patients required in each group.

Details of the planned analysis

~~Individual case forms will be completed by the research coordinator for individual patients.~~ **The research coordinator will complete individual case forms for individual patients.** These forms will be detailing demographic characteristics,

Capital Health

intra-operative, post-operative and follow-up outcomes. Outcome data and blood samples will be collected according a lab/data schedule (Table 2). ~~All data will be reviewed by the appropriate clinical outcomes committee.~~ **The Sponsor will review all data.** Once reviewed all data will entered and maintained electronically.

Primary outcome: Blood component requirement in the two groups will be compared using the Mann-Whitney U test for two independent samples.

Secondary outcomes: Univariate comparisons between patients randomized to FIB and patients randomized to PLACEBO group will be carried out based on pre-, intra-, and post-operative variables using Chi-square tests for dichotomous variables, two-tailed t-tests for continuous variables and Wilcoxon rank sum tests for nominal variables.

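### Minor but wrong as written: the secondary-analysis rule assigns the Wilcoxon rank sum test to nominal variables and plans significance tests on pre-operative variables

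*Combined protocol and SAP*

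**What the plan says.** The rule is one sentence in the STATISTICS section, under Details of the planned analysis, Secondary outcomes. It plans "Univariate comparisons between patients randomized to FIB and patients randomized to PLACEBO group" and says that these "will be carried out based on pre-, intra-, and post-operative variables using Chi-square tests for dichotomous variables", then "two-tailed t-tests for continuous variables and Wilcoxon rank sum tests for nominal variables".

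Nothing elsewhere modifies it. The plan gives no rule for numbering the categories of a nominal variable, names no test for ordinal or skewed variables, and does not say that pre-operative comparisons are descriptive only.

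Two other places matter:

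- **Timing.** The Randomization process section says that "patients will be randomized on the day of surgery after arrival at the OR". The Subject withdrawal criteria place the decision to randomise later, after protamine. On either description the pre-operative values come first.
- **Procedure type.** The Inclusion criteria list AVR+CABG, MVR+CABG, AVR+MVR, redo-sternotomy and aortic root repair with or without AVR. That is a pre-operative variable with five classes and no natural order.

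**The concern.** There are two faults in one sentence.

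First, the Wilcoxon rank sum test compares positions on an ordered scale. For unordered categories the analyst must invent the order by choosing numeric codes, and the p-value then reflects that choice as well as the data. A real difference can also go undetected if the chosen codes happen to balance it out.

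Second, a pre-operative value cannot be affected by a treatment assigned afterwards. A significance test between arms on such a value asks a question that randomisation has already answered. A small p-value there is easily misread as evidence of a problem, and the plan does not say how such a result would be read.

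What is at stake is how secondary and baseline tables are read, and whether two analysts following the text would report the same result. The primary comparison is not at stake.

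**Working it through.** **Arm size.** The secondary rule carries no figure of its own. The illustrations use 111 patients per arm, the Table 1 entry for a 70% reduction at 80% power (222 in total). That entry reproduces: a noncentral-t calculation with a difference of 2.4 units, SD 5.9, two-sided alpha 0.05 and the minimum asymptotic relative efficiency of 0.864 gives 111 per group.

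**Which variables the clause reaches.** With two categories, reversing the codes only changes the sign of the rank statistic, so the two-sided p-value is the same. Those variables go to chi-square in any case. The clause therefore matters only for three or more unordered categories.

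**Three categories, constructed counts.** FIB 50/21/40 and PLACEBO 43/38/30 in categories A/B/C; column totals 93, 59 and 70.

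- Expected FIB rank sum: 111 × 223 / 2 = 12,376.5.
- Variance with tie correction: (111 × 111 / 12) × [223 − Σ(t³ − t) / (222 × 221)]. With Σ(t³ − t) = 1,352,514 this is 200,660, so the SD is 447.95. It is the same for every coding.

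| Order of codes | Mid-ranks A, B, C | FIB rank sum | z | p |
|---|---|---|---|---|
| A < B < C | 47, 123, 187.5 | 50×47 + 21×123 + 40×187.5 = 12,433 | 56.5 / 447.95 = 0.13 | 0.90 |
| A < C < B | 47, 193, 128.5 | 50×47 + 21×193 + 40×128.5 = 11,543 | −833.5 / 447.95 = −1.86 | 0.063 |
| B < A < C | 106, 30, 187.5 | 50×106 + 21×30 + 40×187.5 = 13,430 | 1,053.5 / 447.95 = 2.35 | 0.019 |

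The other three orders are reversals and give the same p-values. Chi-square on the same counts: 2 × (3.5²/46.5 + 8.5²/29.5 + 5²/35) = 6.85 on 2 degrees of freedom, p = 0.032, whatever the coding.

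**Five categories, constructed counts.** FIB 40/15/10/26/20 and PLACEBO 28/22/18/18/25. Over the 120 possible codings the rank sum p-value runs from 0.008 to 0.99, and 26 of 120 (22%) fall below 0.05. Chi-square gives p = 0.10.

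**Power.** In a simulation with assumed category shares of 30/10/30/10/20% against 20/30/10/30/10%, rank sum power was 6% under one coding and over 99% under another. Chi-square power was about 100% under both.

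**Type I error.** With equal shares in both arms and a coding fixed in advance, the simulated rejection rate of the rank sum test was 5.3% over 3,000 runs, which is close to nominal.

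**Pre-operative tests.** A simulated t-test on a variable fixed before randomisation, 111 per arm, rejected in 5.1% of 20,000 runs, which is simply alpha. The baseline column of Table 2 has 12 lines: fibrinogen, hematocrit, hemoglobin, INR/PT, platelet count, PTT, ACT, EXTEM, INTEM, FIBTEM, AT III and ABG. If these were independent and each tested once at 0.05:

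- expected number of false signals: 12 × 0.05 = 0.6;
- chance of at least one: 1 − 0.95¹² = 0.46.

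The range is 40% for 10 tests and 64% for 20. Laboratory values such as hematocrit and hemoglobin are correlated, so the true figure will differ. The 0.05 level is also an assumption, because the plan states it only for the sample size.

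**The case against.** The strongest reply is that nothing of consequence is touched. The named secondary outcomes are laboratory and ROTEM values, lengths of stay, mortality, adverse events, use of factor VII and prothrombin complex, and avoidance of transfusion. None is clearly nominal with three or more levels. Procedure type is pre-operative, and once pre-operative tests are dropped it leaves the scope of the nominal clause too. *Nominal* may also be a slip for *ordinal* or for non-normal data. All of this stands and is why the point is minor. It does not rescue the sentence: the documents nowhere confirm the slip, and an analyst who follows the text would run the wrong test on any multi-category variable.

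Four stronger readings are tempting, and the documents do not support them:

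- **That the tests are invalid or inflate type I error.** With codes fixed in advance the size holds. Error control is at risk only if the coding is chosen after the data are seen.
- **That amounts of factor VII or prothrombin complex are sent to the t-test.** The protocol speaks only of usage, which may be a yes/no record and would then go to chi-square.
- **That baseline p-values will alter the conclusions.** The plan attaches no decision to them, whether adjustment, covariate selection or a change to the primary test.
- **That every baseline difference in the analysed patients is chance.** That is true of all randomised patients. The Unblinding section removes patients unblinded before 24 hours, and the Subject withdrawal criteria remove others, so exact balance in the remaining set is not guaranteed. A baseline significance test does not repair that.

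**Conclusion.** The point holds as a minor correction. The rule as written gives a coding-dependent p-value, and possibly low power, for any variable with three or more unordered categories. It also plans tests on pre-operative variables that cannot inform on treatment.

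The size is illustrative, because all category counts and shares are constructed. The range from 0.019 to 0.90 in the three-category table shows what the coding alone can do; it does not predict a result in this trial. The power loss would matter only for a nominal variable measured after randomisation, and the plan names none. The 46% figure rests on 12 independent tests at an assumed 0.05.

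A reader might infer that a named outcome, the primary result or the trial's error rate is compromised. None of these follows: the Mann-Whitney primary analysis, alpha and the 222 patients are unaffected.

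**What to change.** Replace the sentence under Secondary outcomes with a rule that assigns:

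- chi-square tests, or an exact test where counts are sparse, to dichotomous and nominal variables;
- the Wilcoxon rank sum test to ordinal variables and to clearly skewed quantities, namely CVICU stay, hospital stay, and amounts of factor VII or prothrombin complex if they are recorded as amounts;
- two-tailed t-tests to the remaining continuous variables;
- description by arm, without p-values, to pre-operative variables.

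If *nominal* was meant as *ordinal*, the same text settles it. The cost is one sentence in the statistics section, with no new data and no change to the primary analysis, alpha or sample size.

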- intake of anti-clotting drugs within 2-5 days preoperatively (low dose ASA is allowed) based on the drug's half life or pharmacokinetic profile,
- allergy to concentrated fibrinogen or other components in the product,
- anemia (Hb < 110),
- diagnosed deep vein thrombosis (DVT),
- pulmonary embolism,
- acute stroke **(within the last 3 months)**,
- acute myocardial infarction (within the last 3 months),
- **any unstable medical condition as determined by the Principal Investigator**
- **within the past 30 days, participated in or currently enrolled in a clinical trial.**

Subject withdrawal criteria

Capital Health

As per the intraoperative algorithm (Figure 3) the Anesthesiologist and the Surgeon complete a bleeding assessment ten minutes after the protamine is given. If the patient is not having a diffuse medical bleed they will not be randomized and will be considered a screen failure. **Patients who are experiencing surgical bleeding after weaning from CPB and protamine administration with requirement of a second pump run are withdrawn from the study.** In case of an ongoing bleeding after step 3 of the study algorithm (Figure 3) an immediate and blinded FIBTEM is performed in order to prevent an overdosing of fibrinogen. If the FIBTEM shows an amplitude > 20 mm the patient will be unblinded and drop out of the study for safety reasons. This way it is ensured that a patient who received concentrated fibrinogen is not getting Cryoprecipitate (step 4 of study algorithm; Figure 3) leading to supraphysiologic levels of fibrinogen. Patients who have extremely rare complications like air embolism, heart perforation or heart lung machine failure will be ~~excluded~~ **withdrawn** from the study.

TREATMENT OF SUBJECTS

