Approximately 200 complex cardiac procedures are performed annually in Halifax by nine cardiac surgeons. Of these patients, conflicting studies and patients being disqualified on the basis of exclusion criteria will result in a maximal annual number of eligible patients of 100 per year. We would plan to recruit 222 patients for this study. With a length of follow up of 6 months and using administrative data of an already well established data base we are expecting a rate of loss under 5%.

DATA HANDLING AND RECORD KEEPING

Data will be collected from patient charts and health records, the anesthetic record as well as the Maritime heart center cardiac surgery database. A data collection sheet will be filled out by the study nurse for patients included in the study. Follow-up data will be collected from patients themselves. In cases where patients have adverse outcomes, this information will be obtained from hospital records and the patient.

A data collection form will be used to collect study information and will be completed by the designated study personnel for participants. These forms will be detailing demographic characteristics, intra-operative, postoperative and follow-up outcomes. Individual data forms will record: the perioperative amount of blood products used (packed red cells, FFP, platelets,

Capital Health

Cryo). Also fibrinogen levels, hematocrit, PTT, INR, platelet count, Hemoglobin, Thromboelastometry (ROTEM®, CT, CFT, Angle, MCF), CVICU-stay, Hospital-stay, In-Hospital Mortality, Hemoglobin, adverse events (anaphylaxis, stroke, myocardial infarction, pulmonary embolism, and deep vein thromboembolism) and usage of factor VII concentrate and human prothrombin complex will be collected for study purposes. All data will be reviewed by the appropriate **outcome** committee. Once reviewed all data will be entered and maintained electronically on a designated CDHA computer.

Data will also be collected using the Maritime Heart Center (MHC) cardiac surgery database. This database is a prospectively collected, clinical database that captures detailed information on a wide range of pre-operative, intra-operative, and in-hospital postoperative variables including post-operative complications and in-hospital mortality for all patients undergoing cardiac surgery at the QE II Health Sciences Center.

QUALITY CONTROL AND QUALITY ASSURANCE PROCEDURES

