CFT (clot formation time): time from initiation of clotting until a clot firmness of 20mm is detected
 => fibrin polymerisation, stabilisation of the clot with thrombocytes and F XIII

MCF (maximum clot firmness): firmness of the clot
 => increasing stabilisation of the clot by the polymerised fibrin, thrombocytes as well as F XIII

ML (maximum lysis): reduction of the clot firmness after MCF in relation to MCF
 => stability of the clot (ML < 15%) or fibrinolysis (ML > 15% within 1h)

Figure 2. FIBTEM® Test Specificities

[figure not shown]
[figure not shown]
FIBTEM:

- activation as in **EXTEM**
- platelet inhibition reagent added

TEMogram shows isolated fibrinogen contribution to Clot firmness

- A)
- **EXTEM:** amplitude low
 - **FIBTEM:** amplitude normal
- => fibrinogen level OK
=> platelet deficiency

- B)
- **EXTEM:** amplitude low
 - **FIBTEM:** amplitude low
- => fibrinogen deficiency

[figure not shown]
[figure not shown]

Figure 3. Treatment Algorithm

[figure not shown]

Table 1. Sample Size Calculation

	Relative Risk Reduction in Mean Number of Units Transfused			
Power = 1-beta	30% $\Delta = 1.0$ units (3.4 to 2.4)	50% $\Delta = 1.7$ units (3.4 to 1.7)	70% $\Delta = 2.4$ units (3.4 to 1.0)	90% $\Delta = 3.1$ units (3.4 to 0.3)
80%	634	220	111	69
90%	848	295	149	92
95%	1049	364	183	113

Table 2. Schedule of Assessments

	Preop I+II	Intraop I	Intraop II	Intraop III	Postop I	Postop II	Postop III	Postop IV
Time intervals	Baseline	On Bypass Aortic Clamp Off	Off Bypass After Heparin reversal (5-15 minutes post protamine)	10 minutes after administration (+5 minutes)	End of Surgery (+10 minutes)	Blood Draw 12 Hours (+60 minutes)	Blood Draw 24 Hours (+60 minutes)	Discharge
Primary Outcome					Total Blood Components Used	Total Blood Components Used	Total Blood Components Used	Total Blood Components Used
					Cryo Used	Cryo Used	Cryo Used	Cryo Used
					FFP Used	FFP Used	FFP Used	FFP Used
					Packed Red Cells Used	Packed Red Cells Used	Packed Red Cells Used	Packed Red Cells Used
					Platelets Used	Platelets Used	Platelets Used	Platelets Used
Secondary Outcomes	Fibrinogen Levels		Fibrinogen Levels	Fibrinogen Levels	Fibrinogen Levels	Fibrinogen Levels	Fibrinogen Levels	Adverse Effects
	Hematocrit		Hematocrit	Hematocrit	Hematocrit	Hematocrit	Hematocrit	Anaphylaxis

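### The 222 recruited is exactly 2 × 111, so the 80% power in Table 1 has no reserve for patients the plan itself removes before 24 h; the shortfall is modest

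*Combined protocol and SAP*

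**What the plan says.** **Sample size.** The Sample size section puts the conventional-therapy requirement at a level that "is mean 3.4 units (standard deviation 5.9) based on our data from 2005 to 2007". It applies SD 5.9 to both groups, names the Mann-Whitney U test, uses a two-sided alpha of 0.05 and hypothesises a 70–90% reduction. It states that Table 1 entries are per group. In Table 1 the 70% column ("units (3.4 to 1.0") shows 111 at 80% power.

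**Recruitment.** Estimated Recruitment Rate says "We would plan to recruit 222 patients for this study". In connection with the 6-month follow-up it adds "we are expecting a rate of loss under 5" per cent. No inflation of the number and no replacement of patients is described.

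**Removals.** Under Subject withdrawal criteria, patients with surgical bleeding after bypass "with requirement of a second pump run are withdrawn from the study". Patients whose FIBTEM exceeds 20 mm after step 3 of the algorithm are unblinded and dropped, and those with certain very rare complications are withdrawn. The Unblinding section adds that if treatment is "unblinded before the 24 hour primary end point their data will not be used in the analysis".

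**Timing and interim.** Randomization process places randomisation on the day of surgery after arrival at the operating room. Methodology and Proposed frequency of analysis schedule an interim when half the patients are enrolled, and commit the final analysis to taking it into account.

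**The concern.** A Table 1 entry is the number that must contribute to the primary test. If 222 are randomised and some are then removed by the plan's own rules, fewer than 111 per group are analysed and the 80% is not met on the plan's own calculation. The unblinding rule acts directly on the primary analysis set and also captures the FIBTEM drop-outs. Table 1 also spends the whole 0.05 at the final analysis, although the plan promises an interim adjustment. A non-significant result would then be read against a power figure that belongs to a trial with no removals and no interim.

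**Working it through.** **Inputs from the documents.** Difference 2.4 units (3.4 to 1.0); SD 5.9 in both groups; two-sided alpha 0.05; Mann-Whitney test; 111 per group; 222 in total.

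**Input inferred.** The relative efficiency of the Mann-Whitney test is not stated. The value 0.864 (the minimum asymptotic relative efficiency) is used because it reproduces the table.

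**Formula.** With n per group, let m = 0.864 n. The test is treated as a two-sample t-test with df = 2m − 2 and noncentrality (2.4/5.9) × √(m/2). Power is the noncentral t probability of exceeding the two-sided 5% critical value.

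**Reproducing Table 1.** The smallest n for 80/90/95% power:

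| Difference | Computed | Table 1 |
|---|---|---|
| 1.0 | 634 / 848 / 1049 | 634 / 848 / 1049 |
| 1.7 | 220 / 295 / 364 | 220 / 295 / 364 |
| 2.4 | 111 / 149 / 183 | 111 / 149 / 183 |
| 3.06 (90% of 3.4) | 69 / 92 / 113 | 69 / 92 / 113 |

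All 12 cells match; the last column needs the unrounded 3.06, not the printed 3.1. For the 2.4 column at 80% power, a plain t-test gives 96 and an efficiency of 3/π gives 101, so neither is the plan's basis.

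**No reserve.** For n = 111: m = 95.904, df = 189.8, noncentrality = 0.40678 × √47.952 = 2.817, critical value 1.973, power 80.03%. For n = 110, power is 79.67%.

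**Power by share removed (rates assumed, split equally between arms).**

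| Removed | Per arm | Power |
|---|---|---|
| 0% | 111 | 80.0% |
| 2% | 108.8 | 79.2% |
| 5% | 105.45 | 78.0% |
| 5.4% | 105 | 77.8% |
| 10% | 99.9 | 75.7% |
| 15% | 94.35 | 73.3% |

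If all losses fall in the fibrinogen arm, losing 11 patients gives 77.9% and losing 22 gives 75.3%.

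**At the 90% end.** With a difference of 3.06, power is 94.7% at 111 per arm, 93.5% at 105 and 92.4% at 100.

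**Interim.** The calculation assumes two equally spaced looks, efficacy stopping allowed, overall two-sided alpha 0.05 and a normal approximation. The final drift at 105 per arm is 0.40678 × √(0.864 × 105/2) = 2.740, and the half-way drift is 2.740/√2 = 1.937. Power counts rejection at either look.

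| Boundary (|z|, look 1 / look 2) | 105 per arm |
|---|---|
| None (1.960, final only) | 78.2% |
| O'Brien-Fleming type (2.797 / 1.977) | 77.9% |
| Pocock (2.178 / 2.178) | 73.7% |

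The normal approximation runs about 0.4 points above the noncentral t figure, so only the differences between rows should be read closely.

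**The case against.** **The size is not established.** The plan gives no removal rate for the 24 h endpoint. A reader might apply the loss figure of under 5% to it, but that figure concerns 6-month follow-up, whereas the primary endpoint is collected in hospital. One withdrawal trigger is described as extremely rare. This stands: 5% and 10% are illustrations, and at 5% the loss is about 2 points.

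**The trial is not shown to be underpowered overall.** A reader might infer that it is, but the documents do not support that. The shortfall is at the 70% end only, and Table 1 is conservative in two respects. With efficiency 3/π, power is 83.8% at 111 per arm and 81.8% at 105. Table 1 also uses SD 5.9 for an arm with mean 1.0. As an illustration under an assumed distribution, take negative binomial counts with mean 3.4 and SD 5.9 and keep the same dispersion at mean 1.0. Simulated Mann-Whitney power is then about 97% at 111 per arm and 95% at 100. Neither is the plan's calculation, so neither restores its 80%, but both limit the weight of the point.

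**The interim may cost almost nothing.** No boundary is named, and the documents do not say that the interim may stop for efficacy. A reader might take a Pocock final-look level (0.0294) and compute the power of one test at that level. That overstates the loss because it ignores rejection at the interim.

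**What 222 counts is unclear.** It might mean analysable patients: the Unblinding section counts the interim by 110 participants who have reached the primary endpoint. Also, Subject withdrawal criteria says patients without a diffuse bleed after protamine are not randomised, which conflicts with randomisation on arrival. On that reading, some second-pump-run withdrawals could precede randomisation. If instead patients without a diffuse bleed count among the 222, the loss would be larger. The text settles neither question.

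**Conclusion.** The point holds in a limited form. Recruitment equals the Table 1 requirement exactly, the plan removes patients from the study or the primary analysis before 24 h, and nothing is added for this. On Table 1's own basis power is 80.0% with none removed, about 78% at 5% and about 76% at 10%. At 105 per arm with a half-way look it is about 78% under an O'Brien-Fleming type boundary and about 74% under Pocock.

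These figures rest on the inferred efficiency of 0.864, on assumed removal rates, on 222 meaning randomised patients, and on randomisation at arrival in the operating room. The shortfall is modest and confined to the low end of the hypothesised effect. What is unsupported is the implied 80% as a description of this design; the documents do not show that the trial cannot detect the effect it seeks.

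**What to change.** 1. In Sample size and Estimated Recruitment Rate, state whether 222 means randomised or analysed patients. Give an assumed removal rate before 24 h and the power that results (about 78% at 5% on Table 1's basis).
2. Name the interim boundary, say whether stopping for efficacy is possible, and give power under that boundary.
3. In the Unblinding section, replace the rule that discards data from unblinded patients with a primary analysis of all randomised patients, using their recorded 24 h component use. For patients withdrawn before study drug, define the start of the 24 h window, since it is now counted from administration. This restores 111 per group, but withdrawn patients may dilute the effect, so it does not by itself guarantee 80%; item 2 is still needed.
4. Reconcile Randomization process with Subject withdrawal criteria on when randomisation occurs.

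No extra enrolment is needed. The cost is a few sentences and a slightly less favourable stated power.
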